8.3. Statistical Analysis Methods

8.3.1. Statistical Analysis of PK Concentration

Individual participant concentration data of LEN, GS-5423, and GS-2872 for participants in the PK analysis set will be listed and summarized using descriptive statistics by treatment periods (Day 0 to Week 26, and Week 26 to Week 52). Summary statistics (numbers of participants, mean, SD, coefficient of variation [%CV], median, minimum, maximum, Q1, and Q3) will be presented for individual participant concentration data by time point.

Individual concentration data listings and summaries will include all participants with concentration data. If a participant had quantifiable pre-dose, BLQ at end of infusion, or received incorrect dose, the related PK concentration(s) will be captured in the table but will be excluded from the summary statistics, with reasons for exclusion identified. The sample size for each time point will be based on the number of participants with nonmissing concentration data at that time point. For summary statistics, BLQ values will be treated as zero at predose and postdose time points. The number and percentage of participants with concentration BLQ, as well as an indicator if more than one-third of the participants are BLQ, will be presented for each time point. The method to handle BLQ values for PK summaries are described in Section 3.7. Concentration values will be presented as received from the bioanalytical lab and summary statistics will be presented to three significant digits.

Participants with virologic failure (i.e., HIV-1 RNA \geq 50 copies/mL at Week 26 and 52 visit as defined by the FDA-defined snapshot algorithm) will be flagged in the listings.

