5.3. Dosage and Administration

Treatment Group 1

Dose and administration of LEN, GS-5423, and GS-2872 for Treatment Group 1 are described below and in [Table 4](#).

Day 1:

Participants will receive the following study drugs. All study drugs should be administered on the same day (ie, no visit window is permitted for Day 1 study drug administration).

- Oral LEN 600 mg will be administered orally with approximately 240 mL water, without regard to food.
- SC LEN 927 mg will be administered within 30 minutes after oral LEN, as 2 SC injections at separate injection sites in the abdomen, within 15 minutes.
- GS-5423 2550 mg IV infusion will be administered immediately following (up to 1 hour after) the last SC LEN injection. Infusions of GS-5423 will be administered over 30 minutes.
- GS-2872 2550 mg IV infusion will be administered at least 15 minutes following (up to 1 hour after) the completion of GS-5423 IV infusion. Infusions of GS-2872 will be administered over 30 minutes.

Participants will discontinue their baseline oral ART following administration of the complete study drugs on Day 1.

Day 2:

Participants will self-administer oral LEN 600 mg at home with approximately 240 mL water, without regard to food, at approximately the same time as the oral LEN dose for loading on Day 1.

Weeks 26 and 52:

Virologic suppression (HIV-1 RNA < 50 copies/mL) from the preceding visit must be confirmed prior to proceeding with dosing visits.

Infusions of GS-5423 and GS-2872 will be sequentially administered following SC LEN injection:

- LEN 927 mg, as 2 SC injections at separate injection sites in the abdomen, within 15 minutes
- GS-5423 IV infusion of 2550 mg
- GS-2872 IV infusion of 2550 mg

Every 26 Weeks During the Extension Phase:

At each dosing visit during the extension phase, the following study drugs will be administered:

- LEN 927 mg, as 2 SC injections at separate injection sites in the abdomen, within 15 minutes
- Infusions of GS-5423 and GS-2872 can either be coadministered (preferred option) or administered sequentially (investigator discretion) following SC LEN injection:

— Coadministration

- GS-5423 2550 mg CCI
GS-2872 2550 mg CCI
IV infusion CCI

— Sequential administration

- GS-5423 2550 mg CCI [REDACTED]
[REDACTED] Infusions of GS-5423 will be administered over 30 minutes.
- GS-2872 2550 mg CCI [REDACTED]
[REDACTED] Infusions of GS-2872 will be administered over 30 minutes.

Table 4. Treatment Group 1 Treatment Table

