6.3.11. Assessments for Early Study Drug Discontinuation

6.3.11.1. Early Study Drug Discontinuation During the Randomized Phase

Treatment Group 1:

Participants who discontinue study drug prior to Week 52 should return to the clinic for an early study drug discontinuation (ESDD) visit to be performed within 72 hours of decision to discontinue study drug.

Participants will resume their baseline oral ART (or appropriate regimen selected by the investigator) following ESDD procedures.

Counsel participant regarding the importance of continuing a complete ARV therapy in accordance with standard of care, and refer participant to an appropriate HIV treatment facility, as appropriate.

The participant will be asked to continue to attend scheduled study visits for at least 52 weeks past the last dosing visit.

- If the participant discontinues study drug but continues to attend the scheduled study visits for 52 weeks from their last dosing visit, they will complete all assessments except dosing and complete the study. No further follow-up visits are required.
- The participant is required to attend -follow-up visits at 30, 90, and 180 days after ESDD, as well as every 90 days thereafter until at least 365 days from the last study drug dosing visit. Refer to [Table 1](#) for assessments.

At the 30-, 90-, 180-, and subsequent (referred to as 270- and 365-day) follow-up visits, as applicable, any assessment with abnormal results that the investigator determines to have a possible or probable causal relationship with the study drugs will be repeated weekly (or as often as deemed prudent by the investigator) until the abnormality is resolved, returns to baseline, or is otherwise explained. Gilead may request that certain AEs be followed beyond the protocol-defined follow-up period.

Post ESDD visits are referred to as post study drug (PSD) visits in [Table 1](#).

If a participant discontinues study drug treatment (eg, as a result of an AE), every attempt should be made to keep the participant in the study and continue to perform the required study-related follow-up and procedures (see Section 3.3). If this is not possible or acceptable to the participant or investigator, the participant may be withdrawn from the study.

Treatment Group 3:

Participants who discontinue from the study prior to Week 52 should return to the clinic for an ESDD visit to be performed within 72 hours of decision to discontinue; only a 30-day follow-up visit is required.

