3.1.5. Pharmacokinetic (PK) Analysis Sets

The PK Analysis Sets include the follows:

- LEN PK Analysis Set includes all randomized participants who have received at least 1 dose of study drug, and have at least 1 nonmissing LEN concentration value reported by the PK laboratory test.
- TAB PK Analysis Set includes all randomized participants who have received at least 1 dose of study drug, and have at least 1 nonmissing GS-5423 concentration value reported by the PK laboratory test.
- ZAB PK Analysis Set includes all randomized participants who have received at least 1 dose of study drug, and have at least 1 nonmissing GS-2872 concentration value reported by the PK laboratory test.

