For Pharmacokinetic and Immunogenicity analyses, the nominal visit as recorded on the CRF will be used when data are summarized by visit. Any data relating to unscheduled visits will not be assigned to a particular visit or time point and in general will not be included in by visit summaries. However, the following exceptions will be made:

- An unscheduled visit prior to the first dosing of study drug may be included in the calculation of the baseline value, if applicable.
- For participants who prematurely discontinue from the study drug or complete the study drug, data collected at early study drug discontinuation (ESDD) visit and post study drug follow-up visits will be summarized in the by visit tables.
- Pharmacokinetic and Immunogenicity data collected at Week 52 pre-dose timepoint for the SBR group will be excluded from the by visit summary tables.

3.8.3. Selection of Data in the Event of Multiple Records in an Analysis Visit Window

Depending on the statistical analysis method, single values may be required for each analysis window up to Week 52. For example, change from baseline by visit usually requires a single value, whereas a time-to-event analysis would not require 1 value per analysis window.

If multiple valid, nonmissing measurements exist in an analysis window, records will be chosen based on the following rules if a single value is needed:

- For baseline, the last nonmissing value on or prior to the first dose date of study drug will be selected, unless specified differently. If there are multiple records with the same time or no time recorded on the same day, the baseline value will be the average of the measurements for continuous data (except for HIV-1 RNA, see below), or the measurement with the lowest severity (eg, normal will be selected over abnormal for safety ECG findings) for categorical data.
 - For postbaseline multiple valid non-missing values in an analysis window, records will be chosen based on the following rules if a single value is needed for an analysis window (Particularly for vital signs, weight and BMI, if postbaseline multiple timepoints exist in an analysis window, single values will be required for each protocol specified timepoint of the analysis window based on the following rules): The record closest to the nominal day for that visit will be selected with the exception of CD4 cell counts and CD4% in which the latest record will be selected and HIV-1 RNA level (see below).

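### SAP 8.3.1 does not exclude samples taken after an omitted Week 26 dose, so participants who were not redosed enter the Week 38, 50 and 52 concentration summaries

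*SAP*

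**What the plan says.** **Who is included.** SAP 3.1.5 defines the LEN PK set as "all randomized participants who have received at least 1 dose of study drug, and have at least 1 nonmissing LEN concentration value"; the two antibody sets are built the same way. A Day 1 dose alone is enough. SAP 8.3.1 adds: "Individual concentration data listings and summaries will include all participants with concentration data".

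**How samples are placed.** For PK, SAP 3.8.2 says "the nominal visit as recorded on the CRF will be used when data are summarized by visit". SAP 8.3.1 summarises "by treatment periods (Day 0 to Week 26, and Week 26 to Week 52"), which are calendar periods. Neither rule asks whether the Week 26 dose was given.

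**What is excluded.** SAP 8.3.1: "If a participant had quantifiable pre-dose, BLQ at end of infusion, or received incorrect dose, the related PK concentration(s) will be captured". Such values stay visible as individual entries and are left out of the statistics, with the reason shown. An omitted dose is not named.

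**How undosed samples arise.** Protocol 5.3 sets a condition for the Week 26 and Week 52 doses: "Virologic suppression (HIV-1 RNA < 50 copies/mL) from the preceding visit must be confirmed prior to proceeding with dosing visits". Under Protocol 6.3.9.2.1, participants with detected resistance get no further doses but stay in follow-up. Protocol 6.3.11.1 asks Group 1 participants who stop to attend scheduled visits for at least 52 weeks after the last dosing visit. For those who do, "they will complete all assessments except dosing and complete the study". SAP Table 13-1 schedules serum and plasma PK at Weeks 38, 50 and 52.

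**The concern.** The Week 26 to Week 52 tables and plots will be read as describing exposure after the second dose. A participant dosed only on Day 1 contributes values from a different situation, under the same row labels.

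The low end of the distribution matters in this programme. Protocol 1.4.1.1 argues from antibody levels staying above 10 µg/mL in nearly all participants at 6 months, and Protocol 1.4.2 sets a target for the lower bound of the LEN trough. SAP 8.3.1 reports the minimum, Q1, SD and %CV, and an undosed participant disturbs the minimum most.

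The SAP uses cut-offs based on dosing history elsewhere. Efficacy data in Group 1 stop at 196 days after the last complete regimen or at ART restart (Section 6 and Appendix 2). SAP 3.8.2 removes the control group's Week 52 predose PK from the by-visit tables. No similar rule covers Group 1 participants who were not redosed.

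**Working it through.** The plan gives no figure for this point, so there is none to reproduce. The check has two parts.

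**1. Can such samples reach the Week 38, 50 and 52 rows?**

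- Dosed on Day 1 only: in the PK set (SAP 3.1.5).
- Follow-up to at least 52 weeks after that dose: covers Weeks 38, 50 and 52 (Protocol 6.3.11.1).
- PK drawn at those visits: yes (SAP Table 13-1).
- Counted as randomized-phase data: yes, because SAP Section 3 applies no time limit for anyone who does not enter the extension.
- Removed by the 196-day or ART-restart cut: no, because that cut is written for efficacy.
- Removed by SAP 8.3.1: not on its plain wording.

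Followed as written, the plan includes them. Time since last dose is 266, 350 and 364 days, against 84, 168 and 182 days for a redosed participant.

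**2. How large is the effect?**

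Inputs: 50 participants in Group 1 (Protocol 8.11) and a dosing interval of 182 days. Antibody half-life h (30 to 100 days) and the number not redosed, k, are assumptions; the documents give neither. The model is mono-exponential decline with two equal doses superposed.

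Let x = 2^(−182/h). The ratio of undosed to redosed concentration is r = x/(1 + x), the same at all three visits. The relative fall in the mean is (k/50)(1 − r).

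| h (days) | x | r | Fall, k = 1 | Fall, k = 3 |
|---|---|---|---|---|
| 30 | 0.015 | 0.015 | 2.0% | 5.9% |
| 60 | 0.122 | 0.109 | 1.8% | 5.3% |
| 100 | 0.283 | 0.221 | 1.6% | 4.7% |

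Worked line for h = 60: x = 2^(−3.033) = 0.122; r = 0.122/1.122 = 0.109; for k = 1, 0.02 × 0.891 = 1.8%.

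**Spread.** Assume a CV of 40% among the redosed, p = k/50 and a redosed mean of 1. The mixture variance is (1 − p)(0.16) + p·r²(0.16) + p(1 − p)(1 − r)². For k = 1 and h = 60 this is 0.1568 + 0.0000 + 0.0156 = 0.1724, so SD = 0.415. The mean is 0.982 and the CV is 42.3%, up from 40%. Over h = 30 to 100 it runs from 42.8% to 41.7%.

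**Minimum.** If the redosed values are lognormal with CV 40%, the expected minimum of 50 is about 0.42 of the median. An undosed value of r times typical is then lower by a factor of 0.42/r: about 1.9 at h = 100, 3.9 at h = 60 and 29 at h = 30.

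The model is for the antibodies. For LEN the direction is the same, but no size is claimed, because release from an SC depot does not fit it.

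**The case against.** **The exclusion may already cover it.** An omitted dose could be treated as an incorrect dose, and the SAP does not say otherwise. But the wording concerns a dose that was received, so the ambiguity itself needs a sentence.

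**Few people will follow this route.** HIV-1 RNA at or above 50 copies/mL at Week 24 does not by itself mean never redosed. Protocol 6.3.9.2.1 has retesting, confirmation and possible continuation, and Protocol 5.3.2 allows a restart. Only those who miss the dose entirely and stay on scheduled visits matter. This stands; k may be 0, 1 or 2.

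**The reader can see who was not redosed.** SAP 4.2 tabulates and lists dosing at each visit, and SAP 8.3.1.1 lists sampling details. That helps someone who cross-checks listings, but it does not correct the means, minima or plots.

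Four stronger inferences might be drawn, and the documents do not support them:

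- *That the trough parameter itself is contaminated.* Table 8-1 places the second-interval trough under Week 26 Dosing, and SAP 8.3.2 allows parameters that cannot be estimated to be reported as such and left out. The problem lies in the concentration-by-visit table and plots, which also carry the Week 52 predose row.
- *That the extension dose work rests on these tables.* Protocol 1.4.1.2 uses population PK models and simulation, and itself says no definitive link between exposure and failure can be drawn.
- *That the reported minimum falls in the full ratio 1/r.* That ratio is against a typical redosed value. The lowest of 50 redosed participants is already well below typical.
- *That the early-discontinuation and post-study-drug rows are wrong.* SAP 3.8.2 says "data collected at early study drug discontinuation (ESDD) visit and post study drug follow-up visits will be summarized in the by visit tables", but these carry their own labels and do not enter the Week 38 to 52 rows. Grouping them by time since dose would be a preference.

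Read literally, the exclusion for a quantifiable predose value would also remove every Week 26 and Week 52 predose concentration from the statistics. That cannot be intended, since troughs at both visits are a secondary endpoint. Weeks 38 and 50 are exposed on either reading.

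**Conclusion.** The concern holds for the concentration summaries and mean plots at Weeks 38, 50 and 52, including the Week 52 predose row. As written, the inclusion rule admits samples taken after an omitted Week 26 dose, and the bias in the mean is always downward.

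The size is modest: about 1.6% to 2.0% of the mean per participant among 50, and 4.7% to 5.9% for three. %CV rises by about 2 to 3 percentage points for one participant if the true value is 40%. The minimum is the most sensitive. Medians should barely move, and the Week 26 Dosing parameters and the population PK work are little affected or unaffected.

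These figures rest on an assumed half-life of 30 to 100 days, mono-exponential decline, 50 sampled participants and an assumed number not redosed. The sponsor can replace the last from the dosing records, since Protocol 1.4.1.2 shows the Week 52 data exist.

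**What to change.** In SAP 8.3.1, state that concentrations from visits after Week 26 enter the summary statistics and figures only if the participant received the Week 26 dose of that analyte. Keep all other post-Week 26 values in the listings, marked as not redosed, and report how many participants this concerns for each analyte.

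The condition should be receipt of the Week 26 dose, not dosing at Week 52. A participant who was redosed at Week 26 but does not enter the extension still has a valid Week 52 value.

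In the same edit, limit the exclusion for a quantifiable predose value to the first dose.

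The cost is one flag derived from dosing dates already on the eCRF, and a slightly smaller n at Weeks 38 to 52. No change to data collection is needed.

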PK modeling and simulation based on the data from Studies YCO-0946 and YCO-0971 for GS-5423 and GS-2872 showed that fixed-doses of 2550 or 850 mg of each bNAb are expected to produce similar exposures as 30 or 10 mg/kg weight-based dose, respectively, with no meaningful increase in PK variability, based on the body weight distribution of the target population (with average body weight of 85 kg). Therefore, doses up to 2550 mg IV are expected to be safe for both GS-5423 and GS-2872 in adults with HIV infection.

The antiviral activities of the non-LS forms of each antibody, 3BNC117 and 10-1074, have been studied in multiple Phase 1 studies. In studies in PWH undergoing analytical treatment interruption (MCA-0906 {Mendoza 2018} and MCA-0965 {Gaebler 2022}), it was observed that the virological suppression was generally maintained when serum concentrations of both antibodies were above 10 µg/mL, although the data were limited, as only a single dose level was studied for both bNAbS. It is anticipated that GS-5423 and GS-2872 will demonstrate similar antiviral activity to the unmodified forms (3BNC117 and 10-1074), at the same concentrations based on the location of the amino acid substitutions in the Fc region.

Based on the PK simulations, a single IV dose of 2550 mg GS-5423 or 2550 mg GS-2872 is anticipated to maintain concentrations above 10 µg/mL in nearly 100% of participants at 6 months after dosing. 3BNC117 and 10-1074 have also been studied in viremic PWH as monotherapy and in combination {Bar-On 2018, Caskey 2015, Caskey 2017}. Correlations between serum antibody concentration and viral load reduction at the nadir from these studies suggest the antiviral response is saturated at the concentration range corresponding to the predicted C_{trough} levels maintained with doses of 2550 mg of GS-5423 and 2550 mg of GS-2872 at Week 26, although the data are limited.

The safety and efficacy results from studies with GS-5423 and GS-2872 taken together with PK modeling suggest that 2550 mg flat doses of GS-5423 and GS-2872 are expected to be safe and efficacious in combination with LEN to be evaluated in this Phase 2 study in virologically suppressed adults with HIV-1 infection.

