6.3.6. Pharmacokinetics

Blood sample for the determination of plasma LEN and serum GS-5423 and GS-2872 concentrations will be collected in all participants at scheduled time points. The exact date and time of collection of PK samples must be carefully recorded. PK samples should be drawn from a separate catheter in the opposite arm from the one used for GS-5423 and GS-2872 IV infusions to avoid contamination.

Concentrations of LEN in plasma samples and GS-5423 and GS-2872 in serum samples will be determined using validated bioanalytical methods.

6.3.6.1. Pharmacokinetic Assessments for Treatment Group 1

The following serum PK and plasma PK samples will be collected for all participants in Treatment Group 1:

Serum PK for GS-5423 and GS-2872:

- Day 1: 0 hours (predose, ≤ 30 minutes prior to dosing of oral LEN) and within 5 minutes after the end of the second antibody infusion (GS-2872).
- Week 26: 0 hours (predose, ≤ 30 minutes prior to dosing of SC LEN injection) and within 5 minutes after the end of the second antibody infusion (GS-2872).
- Week 52, and subsequent dosing days through Week 156: 0 hours (predose, ≤ 30 minutes prior to dosing of SC LEN) and within 5 minutes after the end of both antibody infusions (GS-5423 and GS-2872), if coadministered or after the end of the second antibody infusion (GS-2872), if sequentially administered.
- Week 182 and subsequent dosing days: 0 hours (predose, ≤ 30 minutes prior to dosing of SC LEN)
- A single any time sample at other scheduled visits as outlined in [Table 1](#) and [Table 3](#).

Plasma PK for LEN:

- Day 1: 0 hours (predose, ≤ 30 minutes prior to dosing of oral LEN) and within 5 minutes after the end of the second antibody infusion (GS-2872).
- Week 26 and subsequent dosing days: 0 hours (predose, ≤ 30 minutes prior to dosing of SC LEN).
- A single any time sample at other scheduled visits as outlined in [Table 1](#) and [Table 3](#).

6.3.6.2. Pharmacokinetic Assessments for Treatment Group 3

The following serum PK and plasma PK samples will be collected for all participants in Treatment Group 3:

Serum PK for GS-5423 and GS-2872:

- Week 52, Week 130, and Week 156: 0 hours (predose, ≤ 30 minutes prior to dosing of oral LEN) and within 5 minutes after the end of both antibody infusions (GS-5423 and GS-2872), if coadministered or the second antibody infusion (GS-2872), if sequentially administered.

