8.8. Pharmacokinetic Analysis

The serum or plasma concentrations of each analyte (GS-5423, GS-2872, and LEN [and metabolites, if applicable]) over time, including trough concentrations at Weeks 26 and 52 (and other visits, as applicable), will be listed and summarized by nominal time and treatment group using descriptive statistics. PK parameters (AUC_{0-t} , AUC_{last} , $t_{1/2}$, C_{max} , T_{max} , as appropriate) will be listed and summarized by treatment group using descriptive statistics.

Additional population PK analysis and analysis of the relationship between PK and efficacy or safety endpoints may be performed, as appropriate.

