1.1. Study Objectives and Endpoints

Primary Objective	Primary Endpoint

 To evaluate the efficacy of switching to a regimen of lenacapavir (LEN, Sunlenca®), GS-5423, and GS-2872 versus continuing on baseline oral antiretroviral (ARV) therapy (ART) as determined by the proportion of participants with HIV-1 RNA ≥ 50 copies/mL at Week 26 	
 Proportion of participants with HIV-1 RNA ≥ 50 copies/mL at Week 26 as determined by the United States (US) Food and Drug Administration (FDA)-defined snapshot algorithm
Secondary Objectives	Secondary Endpoints

 To evaluate the efficacy of switching to a regimen of LEN, GS-5423, and GS-2872 versus continuing on baseline oral ART as determined by the proportion of participants with HIV-1 RNA ≥ 50 copies/mL at Week 52 To evaluate the efficacy of switching to a regimen of LEN, GS-5423, and GS-2872 versus continuing on baseline oral ART as determined by the proportion of participants maintaining virologic suppression (HIV-1 RNA < 50 copies/mL) at Weeks 26 and 52 	
 Proportion of participants with HIV-1 RNA ≥ 50 copies/mL at Week 52 as determined by the US FDA-defined snapshot algorithm Proportion of participants with HIV-1 RNA < 50 copies/mL at Weeks 26 and 52 as determined by the US FDA-defined snapshot algorithm Changes from baseline in CD4+ T-cell counts at Weeks 26 and 52 Proportion of participants experiencing treatment-emergent adverse events (TEAEs)
Secondary Objectives	Secondary Endpoints

 To evaluate CD4+ T-cell counts at Weeks 26 and 52 To evaluate the safety and tolerability of the 2 treatment groups To evaluate the pharmacokinetics (PK) of GS-5423, GS-2872, and LEN To evaluate the immunogenicity of GS-5423 and GS-2872 	
 Trough concentrations at Weeks 26 and 52 and PK parameters (AUC_{0-t}, AUC_{last}, $t_{1/2}$, C_{max}, and T_{max}) for GS-5423, GS-2872, and LEN as appropriate Incidence of anti-GS-5423 and anti-GS-2872 antibodies

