Natural logarithm transformation will be used for analyzing non-BLQ concentrations and PK parameters in intensive PK samples. Concentration values that are BLQ will be presented as “BLQ” in the concentration data listing. Values that are BLQ will be treated as 0 at predose and postdose time points for summary purposes.

At predose, if all concentration values are BLQ, then the mean, and order statistics (minimum, Q1, median, Q3, and maximum) will be displayed as 0 and the rest of the summary statistics (ie, SD and CV) will be missing. If any values are non-BLQ, then the number of samples, order statistics, and all summary statistics will be displayed.

At any given postdose time point, if more than one-third of the participants have a concentration value of BLQ, then only the number of samples and order statistics will be displayed; otherwise, order statistics and summary statistics will be displayed.

The following conventions will be used for the presentation of order statistics for postdose time points:

- If at least 1 participant has a concentration value of BLQ for the time point, the minimum value will be displayed as “BLQ.”
- If more than 25% of the participants have a concentration data value of BLQ for a given time point, the minimum and Q1 values will be displayed as “BLQ.”
- If more than 50% of the participants have a concentration data value of BLQ for a given time point, the minimum, Q1, and median values will be displayed as “BLQ.”
- If more than 75% of the participants have a concentration data value of BLQ for a given time point, the minimum, Q1, median, and Q3 values will be displayed as “BLQ.”
- If all participants have concentration data values of BLQ for a given time point, all order statistics (minimum, Q1, median, Q3, and maximum) will be displayed as “BLQ.”

Concentration related PK parameters (eg, Clast, Cmax, and Ctau) that are BLQ will be excluded before log transformation or statistical model fitting and displayed as described above.

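### SAP 8.3.1 drops quantifiable pre-dose concentrations from the concentration summaries without limiting this to the first dose, so nearly all Week 26 and Week 52 troughs would leave those tables

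*SAP*

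**What the plan says.** - **Exclusion rule (SAP 8.3.1).** The trigger is "If a participant had quantifiable pre-dose, BLQ at end of infusion, or received incorrect dose". The consequence is that the related concentrations "will be captured in the table but will be excluded from the summary statistics, with reasons for exclusion identified". The sentence names no visit, and the section covers both dosing intervals (Day 0 to Week 26 and Week 26 to Week 52). The same section sets BLQ values to zero in summaries.
- **Display rule (SAP 3.7).** For pre-dose time points: "If any values are non-BLQ, then the number of samples, order statistics, and all summary statistics will be displayed".
- **Endpoint (SAP 1.1, Protocol 2).** A secondary endpoint is "Trough concentrations at Weeks 26 and 52 and PK parameters".
- **Required summary (Protocol 8.8).** The requirement for analyte concentrations reads "including trough concentrations at Weeks 26 and 52 (and other visits, as applicable), will be listed and summarized". The summary is to be given for each nominal time point in each group. The SAP was written against Amendment 3; for this section the Amendment 4 log records only the addition of other visits.
- **Deviations (SAP 8.4).** None are declared for PK.
- **Separate parameter route (SAP Table 8-1 and 8.3.2).** Ctrough is listed after Day 1 dosing and after Week 26 dosing for LEN, GS-5423 and GS-2872, and is summarized with the other PK parameters.

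**The concern.** The exclusion makes sense for the sample drawn before a participant's first dose. A quantifiable value there points to contamination, a mix-up or a sampling error. At a later dosing visit the pre-dose sample has a different meaning: it is the concentration at the end of the preceding 26-week interval, and a quantifiable value is the expected result.

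Because the rule does not separate the two cases, a programmer who follows it removes the values that Protocol 8.8 asks to have summarized. One who ignores it makes an undocumented choice. What is at stake is the pre-dose rows at Weeks 26 and 52 in the concentration tables, possibly the matching points in the mean and median figures, and agreement between those outputs and the Ctrough tables built from the same samples.

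**Working it through.** The plan gives no figure for this point, so there is none to reproduce. The check sets the passages side by side and then sizes the effect.

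**1. Which samples are the troughs.** Protocol 6.3.6.1 schedules a pre-dose sample at Week 26, and at Week 52 and later dosing visits. SAP 3 counts PK data up to and including the pre-dose sample on the first extension dosing date as randomized-phase data. So the Treatment Group 1 troughs at Weeks 26 and 52 are pre-dose samples in the plan's own terms.

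**2. Are they expected to be quantifiable?** Protocol 1.4.1.1 predicts from simulation that a single 2550 mg dose of either antibody keeps concentrations above 10 µg/mL "in nearly 100% of participants at 6 months after dosing". For LEN, Protocol 1.4.2 targets a lower 90% confidence bound for Ctrough of at least 15.5 ng/mL through Week 26. Neither is an observed quantifiable share, and the documents give no lower limit of quantitation. I therefore assume a quantifiable share q of 90% to 100%.

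**3. How many values stay in the summary.** N = 50 planned in Treatment Group 1 (SAP 1.3). As a check on N, 1 − 0.95^50 = 0.923 and 1 − 0.95^25 = 0.723, which match the stated 92.3% and 72.3% for adverse events. Under the literal rule:

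- expected number kept = N × (1 − q)
- chance that none is kept = q^N, treating participants as independent

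| q | Expected number kept of 50 | Chance that none is kept |
|---|---|---|
| 100% | 0 | 1.000 |
| 99% | 0.5 | 0.605 |
| 98% | 1 | 0.364 |
| 95% | 2.5 | 0.077 |
| 90% | 5 | 0.005 |

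Every value kept is BLQ and enters as zero. With the exclusion limited to the first dose, up to 50 of 50 stay at each visit, before discontinuations and missing samples.

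**4. What the table row would show.** If nothing is kept, the row is empty. If only BLQ values are kept and the row is handled as pre-dose, SAP 3.7 displays the mean and the order statistics as 0.

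**5. Consistency with the rest of the plan.**

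- SAP 3.7 provides for non-BLQ values in pre-dose summaries. Under the literal rule none would reach them, so that provision would have no effect.
- SAP 3.8.2 leaves Week 52 pre-dose PK data out of the by-visit tables for the baseline-regimen group only. The plan thus sets a group-specific and visit-specific limit when it wants one, and it sets none for Treatment Group 1.
- Protocol 8.8 requires the summary that the rule empties, while SAP 8.4 declares no deviation.

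**6. Scope of the related concentrations.** The term could mean the pre-dose value alone or the whole dosing-interval profile. On the wider reading, a quantifiable Week 26 pre-dose value would remove that participant's Week 26 to Week 52 profile, which would affect nearly everyone.

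**The case against.** A reader might infer that the secondary endpoint itself is removed. The documents do not support that. SAP Table 8-1 gives Ctrough for both intervals and all three analytes, and says that its parameters serve the PK objectives. SAP 8.3.2 summarizes them more fully than the concentration tables do, adding geometric means and confidence intervals. The exclusions named there are insufficient data and reasons such as an incorrect dose, not a quantifiable pre-dose value. Excluded concentrations also remain listed. This part of the case stands in full.

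Three further arguments stand in part:

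- **Intent.** The trigger reads as a list of anomalies, and the sentence before it says that summaries include all participants with concentration data. Within each period the Week 26 and Week 52 values could be seen as end-of-interval samples. That makes a narrower reading plausible, but the protocol and SAP label these samples pre-dose, and the rule carries no limit.
- **Nature of SAP 3.7.** It governs which statistics are displayed, not which values are included. It still presupposes that quantifiable pre-dose values reach the summary.
- **Figures.** SAP 8.3.1.1 does not say that the exclusions carry over. If they do, it withholds the mean when more than one-third of values are BLQ and the median when more than one-half are. The point would be missing, not plotted near zero.

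It is also tempting to link this rule to the extension-phase dose evaluation in Protocol 1.4.1.2. That work rests on population PK models, and nothing in the documents says that the exclusion from descriptive summaries was applied to them.

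**Conclusion.** The point holds as an internal contradiction in the PK concentration summaries. Applied as written, SAP 8.3.1 removes about 90% to 100% of Treatment Group 1 troughs from the concentration tables at each of Weeks 26 and 52, leaving about 0 to 5 zeros out of 50. The same applies to the mean and median figures only if they use the same exclusions. The tables would then disagree with the Ctrough tables in both sample size and values.

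The size rests on the assumed 90% to 100% quantifiable share and on all 50 planned participants giving a sample at each visit. The contradiction itself rests on neither. This is more than missing detail, because a stated rule gives a wrong table when followed. It does not cost the trial its trough endpoint, and it does not touch the primary endpoint or the safety analyses.

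**What to change.** In SAP 8.3.1:

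1. Limit the pre-dose trigger to a quantifiable concentration before the participant's first dose of that analyte, which is Day 1 for Treatment Group 1.
2. Define the related concentrations for each trigger: the single sample or the dosing-interval profile.
3. State that Treatment Group 1 pre-dose values at Weeks 26 and 52 are troughs and are kept in the concentration summaries and figures.
4. State in SAP 8.3.1.1 whether the exclusions apply to the figures.

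The cost is a few sentences and no new data. If Week 52 outputs already exist, compare the sample sizes in the Week 26 and Week 52 pre-dose rows with those in the Ctrough tables. Rerun the concentration tables only if the literal rule was applied.
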